**Section scores**

Recorded Physical function score  
 Recorded Role-Physical score  
 Recorded Body pain score  
 Recorded General Health score  
 Recorded Vitality score  
 Recorded Social functioning score  
 Recorded Role-Emotional score  
 Recorded Mental Health score

**Summary scores**

Physical components score (PCS)  
 Mental component score (MCS)

• Haemodynamic assessment:

- Mean values of the readings taken for the Duplex ultrasonography measure at baseline and 3 months. In the control group, only resting values will be undertaken over a 3-minute period. The intervention group will have these parameters measured at rest, at 15 and 30-minutes into device use and then at 1 and 5 minutes after device cessation [9].
  - Mean Volume Flow (VF, cc/min) for one leg (Right or Left) for each patient.
  - Mean Time average Mean Velocity (TAMV, cm/s) for one leg (right or left)
- Mean values of the readings (before use, during use and after use for the Device group and at rest for the Control group) taken for the Laser Doppler Flowmetry (LDF) measure at baseline,3,6 and 12 months
  - Mean Blood flux for one leg (Left or Right)
- Ankle Brachial Pressure Index (ABPI) measure at baseline,3,6 and 12 months for the Left and Right Ankle

• Compliance with interventions. All compliance measures below will be summarized from each participant's personalized diary.

**Supervised Exercise Therapy (SET) measured weekly from baseline to treatment, the duration of which will vary from 2 months to 6 months depending on local policy (see Appendix 3).**

Total number of weeks of exercise (summarized from each participant's personalised diary).  
 Number of therapy sessions attended each week  
 Total minutes of exercise at home each week

**Device - Neuromuscular Electrical Stimulation (NMES) measured daily from baseline to 3 months**

Number of minutes of the NMES device use for each day  
 Intensity setting of the NMES device for each day's use  
 Some devices have a data logger that will record usage each time. Information will be recorded and uploaded at the 3 months follow up.

**Exercise Advice (EA) measured weekly from baseline at 3 months**

Recorded number of weeks of exercise reported in diary  
 Recorded total minutes of exercise at home per week

• Device experience questionnaire

A simple device use questionnaire will be administered by device users to report their subjective experience with the device. The questionnaire contains 6 questions:

- Overall, how easy did you find the device to use?
- Do you think the device helped to lessen the pain?
- Do you think you can walk further?
- Did you use the device as instructed?
- Do you think you could have used the device more often than you did?

Imperial Clinical Trials Unit	STATISTICAL ANALYSIS PLAN	NESIC
-------------------------------	---------------------------	-------

- Did you use the device beyond the 3 months treatment?
- Compliance Classification for each of SET, NMES and EA.

### 7.5 Safety Variables

**Adverse Event (AE).** An AE is any untoward medical occurrence, unintended disease or injury or any untoward clinical signs (including abnormal laboratory findings) in subjects, users or other persons whether or not related to the investigational medical device.

**Adverse Device Effect (ADE).** An ADE is an adverse event related to the use of an investigational medical device resulting from insufficiencies or inadequacies in the instructions for use, the deployment, the implantation, the installation, the operation, or any malfunction of the investigational medical device and/or the result of a use error or intentional misuse.

To assess patient and study safety the following variables of AE/ADE will be analysed:

- Severity of Adverse Events
- Relationship to device
- Outcome
- SAE classification
- Site

**Serious Adverse Events (SAE).** A Serious Adverse Event (SAE) is defined as any adverse event that has:

- a) Led to a death
- b) Led to a serious deterioration in health that either:
  - i) Resulted in a life-threatening illness or injury, or
  - ii) Resulted in a permanent impairment of a body structure or a body function, or
  - iii) Required in-patient hospitalisation or prolongation of existing hospitalisation, or
  - iv) Resulted in medical or surgical intervention to prevent life threatening illness or injury or permanent impairment to a body structure or a body function
- c) Led to foetal distress, foetal death or a congenital abnormality or birth defect.

These includes device deficiencies that might have led to a serious adverse event if a) suitable action had not been taken or b) intervention had not been made or c) if circumstances had been less fortunate.

**Serious Adverse Device Effect (SADE).** A SADE is an adverse device effect that has resulted in any of the consequences characteristic of a serious adverse event or that might have led to any of these consequences if suitable action had not been taken or intervention had not been made or if circumstances had been less opportune. SADEs can be classified into either Anticipated Serious Adverse Device Effects (ASADE) or Unanticipated Serious Adverse Device Effects (USADE).

To assess patient and study safety the following variables of SAE/SADE will be analysed:

- Reasons
- Severity of Adverse Events
- Outcome
- Causal Relationship to device
- Action taken
- Site

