## 7.6 Serious Adverse Event (SAE)

### 7.6.1 Serious Adverse Event Definition

**Serious Adverse Event (SAE)** is any adverse event that has

- a) Led to a death
- b) Led to a serious deterioration in health that either:
  - i) Resulted in a life-threatening illness or injury, or
  - ii) Resulted in a permanent impairment of a body structure or a body function, or
  - iii) Required in-patient hospitalisation or prolongation of existing hospitalisation, or
  - iv) Resulted in medical or surgical intervention to prevent life threatening illness or injury or permanent impairment to a body structure or a body function
- c) Led to foetal distress, foetal death or a congenital abnormality or birth defect

Imperial Clinical Trials Unit	NESIC Clinical Study Protocol V6.0 24/03/2020	Form Number CR001A-T
-------------------------------	---	-------------------------

This includes device deficiencies that might have led to a serious adverse event if a) suitable action had not been taken or b) intervention had not been made or c) if circumstances had been less fortunate. These are handled under the SAE reporting system.

A planned hospitalisation for pre-existing condition, or a procedure required by the protocol, without a serious deterioration in health, is not considered to be a serious adverse event.

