## **7.12 Pregnancy**

Where relevant, any pregnancy occurring during the clinical study and the outcome of the pregnancy should be recorded on a pregnancy notification form patients will be asked to consent to be followed up for congenital abnormality or birth defect. Pregnancy is considered an SAE, the patient will be asked to stop using the device, followed up according to the protocol and the results analysed as per intention to treat.

Imperial Clinical Trials Unit	NESIC Clinical Study Protocol V6.0 24/03/2020	Form Number CR001A-T
-------------------------------	---	-------------------------

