### **8.5 Safety Analysis**

All safety variables will be summarized by treatment in the form of frequency tables for categorical variables or descriptive statistics for continuous variables. The tables will be produced using all randomized patients.

A list of all Protocol Deviations, Concomitant Medications, Adverse Events and Serious Adverse Events will be produced (see Section 8.9.8).

Imperial Clinical Trials Unit	STATISTICAL ANALYSIS PLAN	NESIC
-------------------------------	---------------------------	-------

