**Table 83 Summary of Serious Adverse Events by treatment**

Variable N(%)	Treatment  : NMES + EA and NMES+EA+SET N=(XX)	Control  : EA and EA+SET N=(XX)	Total N=(XX)
Severity			
Mild	XX (XX.X%)	XX (XX.X%)	XX (XX.X%)
Moderate	XX (XX.X%)	XX (XX.X%)	XX (XX.X%)
Severe	XX (XX.X%)	XX (XX.X%)	XX (XX.X%)
Life threatening or disabling	XX (XX.X%)	XX (XX.X%)	XX (XX.X%)
Fatal	XX (XX.X%)	XX (XX.X%)	XX (XX.X%)
Outcome			
Recovered	XX (XX.X%)	XX (XX.X%)	XX (XX.X%)
Recovering/Improving	XX (XX.X%)	XX (XX.X%)	XX (XX.X%)
Not recovered	XX (XX.X%)	XX (XX.X%)	XX (XX.X%)
Fatal	XX (XX.X%)	XX (XX.X%)	XX (XX.X%)
Not assessable	XX (XX.X%)	XX (XX.X%)	XX (XX.X%)
Causal Relationship to device			
Definitely	XX (XX.X%)	XX (XX.X%)	XX (XX.X%)
Probably	XX (XX.X%)	XX (XX.X%)	XX (XX.X%)
Possibly	XX (XX.X%)	XX (XX.X%)	XX (XX.X%)
Unlikely	XX (XX.X%)	XX (XX.X%)	XX (XX.X%)
Not related	XX (XX.X%)	XX (XX.X%)	XX (XX.X%)
Not assessable	XX (XX.X%)	XX (XX.X%)	XX (XX.X%)
Site Name			
Cambridge University Hospital	XX (XX.X%)	XX (XX.X%)	XX (XX.X%)
Dorset County Hospital	XX (XX.X%)	XX (XX.X%)	XX (XX.X%)
Hull and East Yorkshire Hospitals	XX (XX.X%)	XX (XX.X%)	XX (XX.X%)
Imperial College Healthcare	XX (XX.X%)	XX (XX.X%)	XX (XX.X%)
Newcastle Upon Tyne Hospitals	XX (XX.X%)	XX (XX.X%)	XX (XX.X%)
North Bristol	XX (XX.X%)	XX (XX.X%)	XX (XX.X%)
Nottingham University Hospitals	XX (XX.X%)	XX (XX.X%)	XX (XX.X%)
Royal Bournemouth & Christchurch	XX (XX.X%)	XX (XX.X%)	XX (XX.X%)
Hospital			
St George's University Hospitals	XX (XX.X%)	XX (XX.X%)	XX (XX.X%)
Taunton & Somerset	XX (XX.X%)	XX (XX.X%)	XX (XX.X%)
University Hospital Southampton	XX (XX.X%)	XX (XX.X%)	XX (XX.X%)

Treatment: NMES + Local Available Exercise Therapy (NMES+EA and NMES+EA+SET)Control: Local Available Exercise Therapy (EA and EA+SET)

Imperial Clinical Trials Unit	STATISTICAL ANALYSIS PLAN	NESIC
-------------------------------	---------------------------	-------

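### Table 83 does not separate device deficiencies that led to no serious event from SAEs with an actual serious outcome, so the device-arm SAE count may be inflated

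*SAP*

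**What the plan says.** - **SAP 7.5, core definition.** "A Serious Adverse Event (SAE) is defined as any adverse event that has" led to death, to a serious deterioration in health, or to foetal harm: criteria (a) to (c). Each criterion needs something that happened.
- **SAP 7.5, extension.** "These includes device deficiencies that might have led to a serious adverse event if a) suitable action had not been taken", with two further conditions of the same kind.
- **SAP 7.5, SADE.** A SADE is an adverse device effect with the consequences of an SAE, or one "that might have led to any of these consequences if suitable action had not been taken or intervention had not been made".
- **Protocol 7.6.1.** The same extension stands in the protocol's definition ("This includes device deficiencies that might have led to a serious adverse event if a" and so on). It is followed by a sentence that the SAP leaves out: "These are handled under the SAE reporting system".
- **SAP 8.5.** "All safety variables will be summarized by treatment in the form of frequency tables for categorical variables". The tables use all randomised patients. No between-arm test or interval is planned for SAEs.
- **SAP Table 83**, titled "Summary of Serious Adverse Events by treatment". Its row blocks are severity, outcome, causal relationship to device, and site. SAP 7.5 also lists reasons and action taken as SAE/SADE variables for analysis, but the table has neither.
- **SAP Tables 84 and 85.** The SAE listing takes the layout of the adverse event listing, whose columns include event description, outcome, SAE classification and reason.
- **SAP 5.3.** Controls are assigned the locally available exercise therapy only. The device is assigned to one arm.

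**The concern.** A rule that sends potential hazards down the SAE route serves prompt reporting. When the same rule decides what is counted in a by-arm table, it can mix two different things: patients who had a serious outcome, and devices that failed without causing one. The second kind belongs, by assignment, to one arm. Any such case therefore moves the device column up and leaves the control column where it is.

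At stake is how the SAE summary of a home-use device reads. A reader of Table 83 could take a small excess in the device arm for harm to patients when part of it is equipment faults. In the device-related rows the control column is expected to be near zero anyway. The difficulty there is that potential and actual serious events would share a row, and not that a comparison is biased.

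**Working it through.** **1. Does the counting rule admit cases with no serious event?** Criteria (a) to (c) require an outcome. The extension covers deficiencies that might have led to an SAE if circumstances had been different. Read together, the extension adds cases that fail (a) to (c). The rule says nothing about lesser harm, so such a case may or may not have involved a minor injury.

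**2. Can Table 83 separate them?** Its severity rows run from mild to fatal, its outcome rows from recovered to not assessable, its causality rows from definitely to not assessable, and the rest are sites. None identifies a deficiency.

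**3. Which arm can contribute?** By assignment, only the device arm (SAP 5.3).

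**4. Denominator.** The plan states 86 per group before dropout and 96 per arm after it (SAP 5.7). A two-sample t calculation with difference 60 m, SD 120 m, two-sided alpha 0.05 and 90% power gives 85.03, which rounds up to 86. Then 86/(1 − 0.10) = 95.6, which rounds up to 96. The planned figure reproduces.

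**5. Size per case.** For k device-arm patients counted only because of a deficiency, the added percentage is 100 × k/96. The documents give no k; these values are assumed:

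- k = 0: 0
- k = 1: 1.0 point
- k = 3: 3.1 points
- k = 5: 5.2 points

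**6. Size as a rate.** Let p be the true SAE risk, equal in both arms, and d the proportion of device-arm patients with such a deficiency, independent of p. Both are assumptions. The device-arm proportion becomes q = 1 − (1 − p)(1 − d), and the difference from control is q − p = d(1 − p). Expected counts out of 96:

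| p | Control | Device, d = 0 | d = 1% | d = 2% | d = 5% | d = 10% |
|---|---|---|---|---|---|---|
| 5% | 4.8 | 4.8 | 5.7 | 6.6 | 9.4 | 13.9 |
| 10% | 9.6 | 9.6 | 10.5 | 11.3 | 13.9 | 18.2 |
| 15% | 14.4 | 14.4 | 15.2 | 16.0 | 18.5 | 22.6 |

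The difference is 0 at d = 0, about 0.9 to 1.0 point at d = 1%, 4.3 to 4.8 points at d = 5%, and 8.5 to 9.5 points at d = 10%. With the deficiencies shown separately, the expected counts under equal true risk are equal in every row (the d = 0 column).

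**The case against.** The strongest case is that this is a gap in a table layout and no more. The SAP's clause matches the protocol's, which itself stands under a heading that calls it a definition, so the documents agree on it. The tables are descriptive. Reasons are already listed for analysis in SAP 7.5, and the SAE listing gives a description, classification and reason for each case. With a handful of cases a reader could sort them by hand.

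Much of this stands. There is no conflict between the documents on the clause, and no reason to change the definition. But agreement on a definition does not correct the summary count, and the documents do not say that the reason column identifies deficiencies. A by-arm summary should not need to be rebuilt from a listing.

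Some stronger readings are tempting but not supported:

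- *The counts are inflated.* No deficiency rate is given, and at zero deficiencies nothing changes.
- *The deficiencies harmed nobody.* The text implies only that no serious event resulted.
- *They would be coded as definitely or probably related.* Protocol 7.5 grades the link between device use and an adverse event. The documents do not say how a deficiency with no event is graded, and Table 83 has a not-assessable row.
- *The SADE wording also brings in faults with no event.* A SADE must first be an adverse device effect, which is an adverse event. The wording extends only the seriousness of something that occurred.
- *Pregnancy adds to the bias.* Protocol 7.12 states "Pregnancy is considered an SAE", and SAP 7.5 does not repeat it. That is a separate mismatch with no direction by arm. Its reach looks negligible, because pregnancy is an exclusion and participants must be of non-childbearing potential or use contraception and test negative.
- *Controls can never contribute.* This is true by assignment, but Table 6 has a deviation row for a patient who bought a device, without saying in which arm.

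**Conclusion.** The point holds as a possibility with a known direction. Under the SAP's counting rule, a deficiency that led to no serious event enters the SAE count. By assignment it can enter only in the device arm, and Table 83 does not show it separately. The device-arm figure may be raised by about 1.0 percentage point for each such patient out of 96, and by nothing if none are reported. The larger figures in the working rest on assumed deficiency and SAE rates, on independence between the two, and on the planned 96 per arm. They illustrate scale and are not forecasts. No test, p-value or primary result depends on this. The change is still worth making, because it costs almost nothing and makes the SAE summary mean what a reader will take it to mean.

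**What to change.** Leave the SAE definition and every site and sponsor reporting duty as they are. Change only how the cases are tabulated:

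1. In Table 83, tabulate by arm the SAEs that meet criteria (a) to (c).
2. Add a separate device-arm line for device deficiencies with SAE potential but no serious outcome.
3. Use the Reasons variable that SAP 7.5 already lists to assign cases, after confirming that it records deficiencies. If it does not, the classification and description columns of the SAE listing are the next place to look.
4. Distinguish SADEs with an actual serious outcome from those that only might have had one.
5. Say in SAP 8.5 that Table 83 is split in this way.

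The cost is a few sentences and one or two table lines. If Reasons or the listing identifies the cases, no new data are needed.

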### Protocol deviation and violations

- Protocol Deviation or Violation
- Any Protocol Deviation or Violation by Site
- Type of Protocol Deviation

### Concomitant medication

## 8. Statistical Methodology

The planned analyses for all the endpoints are summarised in Table 2 below.

**Table 2 Endpoints and related planned Statistical Analysis Summary**

	End Point	Model
Continuous	Absolute walking distance (AWD) measured by treadmill testing at 3 months (censored at 15 mins and the distance reached to this point is 790 metres) **	Tobit Regression for Absolute walking distance (AWD) at three months with AWD at baseline, treatment indicator, centre and group (SET vs non-SET) as covariates.
	Proportion of patients whose absolute walking distance at 3 months improved by 60 metres or more from baseline	Chi-square test at 3 months
	Proportion of patients whose absolute walking distance at 3 months improved by 100 metres or more from baseline	Chi-square test at 3 months
	Absolute walking distance (AWD) measured at 3, 6, and 12 months. This variable is censored at 15 mins and the distance reached to this point is 790 metres.	Multilevel Tobit model, treating patient as a random effect (repeated measurement) to investigate the relationship between AWD and covariates: AWD baseline measurement Treatment Time Time*Treatment interaction, Centre Group (SET vs non-SET) Age Gender BMI Smoking status
	The proportion of patients who improved AWD at each time point by 
 
• 60 metres or more from baseline
 
• 100 metres or more from baseline
 
	Table of proportion of AWD improvements by treatment and by visit.
Continuous	Initial claudication distance (ICD) measured at 3, 6 and 12 months. This variable is censored at 15 mins and the distance reached to this point is 790 metres.	Multilevel Tobit model Linear mixed-effects model, treating patient as a random effect (repeated measurement) to investigate the relationship between ICD and covariates: ICD baseline measurement Treatment Time Time*Treatment interaction Centre Group (SET vs non-SET) Age Gender BMI
	The proportion of patients who improved ICD at each time point by 
 
• 60 metres or more from baseline
 
• 100 metres or more from baseline
 
	Table of proportion of ICD improvements by treatment and by visit.

Imperial Clinical Trials Unit	STATISTICAL ANALYSIS PLAN	NESIC
-------------------------------	---------------------------	-------

	Quality of Life (QoL)	
	ICQ health score (calculated using the formulas in Appendix 2 measured at 3, 6 and 12 months	Plot of mean ICQ health score change over time by treatment arm (mean and SD). ANCOVA model for ICQ health score on treatment group indicator, controlling for ICD baseline measurement.
	EQ-5D-5L health score measured at 3, 6 and 12 months	Plot of mean EQ-5D-5L health score changes over time by treatment arm (mean and SD). ANCOVA model for EQ-5D-5L health score on treatment group indicator, controlling for EQ-5D-5L baseline measurement.
	SF36-scores (obtained using software Appendix 2) measured at 3, 6 and 12 months	Plot of mean SF36-scores change over time by treatment arm (mean and SD).
	Section scores Physical function score Role-Physical score Body pain score General Health score Vitality score Social functioning score Role-Emotional score Mental Health score	Separate ANCOVA models for SF36 scores on treatment group indicator, controlling for the baseline measurement of the outcome being analysed.
	Summary scores Physical component scores (PCS) Mental component scores (MCS)	
	Haemodynamic AssessmentT	
	Duplex ultrasonography measure at baseline and 3 months • Mean Volume Flow (VF, cc/min) for one leg (either Right or Left) for each patient • Mean Time average Mean Velocity (TAMV, cm/s) one leg (Left or Right) 2 models	Separate Linear regression models for the Duplex ultrasonography measurements (MVF and MTAMV), using as covariates: Specific baseline measurement Treatment Time Time*Treatment interaction Centre Group (SET vs non-SET) Age Gender BMI
	Laser Doppler Flowmetry (LDF) measure at baseline, 3, 6 and 12 months • Mean Blood flux for one leg (Left or Right)	Separate ANCOVA models for the variables of Laser Doppler Flowmetry (LDF) on treatment group indicator, controlling the baseline measurement of the outcome being analysed.
	Ankle Brachial Pressure Index (ABPI) measure at baseline, 3, 6 and 12 months ABPI for the Left Ankle ABPI for the Right Ankle	Separate ANCOVA models for the variables of Ankle Brachial Pressure Index (ABPI) on treatment group indicator, controlling the baseline measurement of the outcome being analysed.

Compliance with interventions		
Continuous	Supervised Exercise Therapy (SET) measured weekly from baseline to 3 months (recorded in participant's personalised diary) 
 
• Total number of weeks of exercise
 
• Number of therapy sessions attended each week
 
• Total minutes of exercise at home each week
 
	Summary in a table by treatment group. -Mean (SD) -Median (IQR)
	Neuromuscular electrical stimulation measured daily from baseline to at 3 months (recorded in participant's personalised diary) 
 
• Number of minutes of the NMES device use for each day
 
• Intensity setting of the NMES device for each day's use
 
	Summary in a table by treatment group. -Mean (SD) -Median (IQR)
	Exercise Advice (EA) measured weekly from baseline to 3 months (recorded in participant's personalised diary) 
 
• Recorded number of weeks of exercise reported in diary
 
• Recorded total minutes of exercise at home per week
 
	Summary in a table by treatment group. -Mean (SD) -Median (IQR)
Categorical	Device experience questionnaire(6 questions on patient experience using the devices)	Table of summary statistics
	Compliance	Table of proportion of compliance by treatment.
Subgroup Analysis Summary		
Continuous	Estimate the treatment effect in the SET vs the non-SET groups, at 3 months  Subgroup analysis 1: SET vs non-SET groups (NMES+SET+EA & SET+EA vs NMES+EA & EA).  Proportion of patients whose absolute walking distance at 3 months improved by 60 metres or more from baseline  Proportions of patients whose absolute walking distance at 3 months improved by 100 metres or more from baseline	Tobit Regression for absolute walking distance at 3 months with AWD at baseline , Treatment, Centre and Group as covariates.  Chi-square test at 3 months  Chi-square test at 3 months
	Estimate the treatment effect of NMES in the SET and non-SET groups, at 3 months  Subgroup analysis 2: NMES in the SET (NMES+SET+EA vs SET+EA)  Subgroup analysis 3: NMES in the non-SET (NMES+EA vs EA)  For both subgroups we will calculate:	Tobit Regression for absolute walking distance at 3 months with AWD at baseline ,Treatment, Centre and Group as covariates.

Imperial Clinical Trials Unit	STATISTICAL ANALYSIS PLAN	NESIC
-------------------------------	---------------------------	-------

	
 
• Proportion of patients whose absolute walking distance at 3 months improved by 60 metres or more from baseline
 
• Proportions of patients whose absolute walking distance at 3 months improved by 100 metres or more from baseline
 
	Chi-square test at 3 months
	Investigate if NMES+EA has similar effect as SET+EA, at 3 months	Chi-square test at 3 months
	Subgroup analysis 4: NMES+EA vs SET +EA	Tobit Regression for absolute walking distance at 3 months with AWD at baseline, Treatment, Centre and Group as covariates.
	Proportion of patients whose absolute walking distance at 3 months improved by 60 metres or more from baseline	Chi-square test at 3 months
	Proportions of patients whose absolute walking distance at 3 months improved by 100 metres or more from baseline	Chi-square test at 3 months
	To determine if NMES+SET+EA is more effective than NMES+EA, at 3 months.	Tobit Regression for absolute walking distance at 3 months with AWD at baseline, Treatment, Centre and Group as covariates.
	Subgroup analysis 5: NMES+SET+EA vs NMES+EA	Chi-square test at 3 months
	Proportion of patients whose absolute walking distance at 3 months improved by 60 metres or more from baseline	Chi-square test at 3 months
	Proportions of patients whose absolute walking distance at 3 months improved by 100 metres or more from baseline	Chi-square test at 3 months

\*\*Primary outcome

T Mechanistic outcome

Summaries of continuous variables will be presented as mean and standard deviations if normally distributed, and as medians and inter-quartile ranges for skewed data. Categorical variables will be presented as frequencies and percentages in the form of summary tables.

All statistical tests will be two-tailed with a 5% significance level.

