for one leg (either the left or right) at 3 months, between the intervention group and the control group, using the baseline value of the specific measurement, the treatment indicator variable, centre, group (SET vs non-SET), age, gender and BMI as covariates. Results of these regression models will be presented in tables (see Section 8.9.6.3).

Laser Doppler Flowmetry (LDF), Duplex ultrasonography (DU) measurements, (Mean Volume Flow and Mean Time Average Mean Velocity) and Ankle Brachial Pressure Index (ABPI) for Left and Right Ankle from the Haemodynamic assessment will be analysed using separated Analysis of Covariance (ANCOVA) models.

Analysis of Covariance (ANCOVA) models for the Haemodynamic assessment for both Laser Doppler Flowmetry (LDF) and Ankle Brachial Pressure Index (ABPI) will be analysed, on treatment group indicator, controlling for the baseline measurement of the outcome assessment being analysed. They will be used to explore changes over time and assess the difference between the two treatment groups. Result of these ANCOVA models will be presented in tables (see Section 8.9.6.3).

The information collected with regards to compliance will be summarized by treatment. The information will be displayed in 3 different tables, one for each intervention: Exercise Advice (EA) compliance, Supervised Exercise Treatment (SET) compliance and the Neuromuscular Electrical Stimulation device (NMES) compliance. (Section 8.9.6.4).

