### 8.9.6.3 Haemodynamic Assessment

**Table 39 Summary of Duplex ultrasonography (Mean Volume flow – measured in one leg) by Time and Treatment**

Time	Treatment	N	Mean	SD	Median	Min	Max
Baseline	Treatment  : NMES + EA and NMES+EA+SET	XX	XX.XX	XX.XX	XX	XX	XX
	Control  : EA and EA+SET	XX	XX.XX	XX.XX	XX	XX	XX
	Treatment  : NMES + EA and NMES+EA+SET	XX	XX.XX	XX.XX	XX	XX	XX
3 months	Control  : EA and EA+SET	XX	XX.XX	XX.XX	XX	XX	XX

The average value of the 5 readings taken from the Volume Flow for the measured in one leg by patient in the Device group is presented in the table.

Treatment: NMES + Local Available Exercise Therapy (NMES+EA and NMES+EA+SET)

 Control: Local Available Exercise Therapy (EA and EA+SET)

**Table 40 Output of Linear Regression Model for Duplex ultrasonography (Mean Volume flow – measured in one leg) at 3 months**

Variable	Coefficient	SE	t	P> t	Confidence interval
Mean-DU - VF(Baseline)	XX.XX	XX.XX	X.XX	X.XXX	X.XX
Treatment	XX.XX	XX.XX	X.XX	X.XXX	X.XX
Centre	XX.XX	XX.XX	X.XX	X.XXX	X.XX
Group	XX.XX	XX.XX	X.XX	X.XXX	X.XX
Age	XX.XX	XX.XX	X.XX	X.XXX	X.XX
Gender	XX.XX	XX.XX	X.XX	X.XXX	X.XX
BMI	XX.XX	XX.XX	X.XX	X.XXX	X.XX
_cons	XX.XX	XX.XX	X.XX	X.XXX	X.XX

R-square = X.XX Adj R-Squared=X.XX Prob>F=X.XX

Linear regression model: Mean DU -Volume flow (VF) measured in one leg at 3 months = intercept + Mean-VF (Baseline) + Treatment + Centre + Type + Age + Gender + BMI + residual error. Treatment=NMES + local available Exercise therapy vs. local available Exercise therapy only (1,0), Group= Set or Non-SET group (1,0), Centre=centre identifier.

**Table 41 Summary of Duplex ultrasonography (Mean Time Average Mean Velocity – measured in one leg) by Visit and Treatment.** Same display as Table 39, but for Duplex ultrasonography (Time average mean velocity – measured in one leg).

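### SAP Table 2 gives duplex flow a model with Time and Time*Treatment although there is only one follow-up, contradicting SAP 8.3.1 and Tables 40 and 42

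*SAP*

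**What the plan says.** SAP section 8 presents Table 2 as the summary of planned analyses for every endpoint and marks haemodynamics as the mechanistic outcome. Four descriptions of the duplex model can be found.

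- **SAP Table 2.** The endpoint cell reads "Duplex ultrasonography measure at baseline and 3 months". The model cell reads "Separate Linear regression models for the Duplex ultrasonography measurements (MVF and MTAMV), using as covariates: Specific baseline measurement Treatment Time Time*Treatment interaction", followed by centre, group, age, gender and BMI. No patient random effect is named, whereas the AWD and ICD rows name one.
- **SAP 8.3.1 and Tables 40 and 42.** The 3-month value is compared between arms "using the baseline value of the specific measurement, the treatment indicator variable, centre, group (SET vs non-SET), age, gender and BMI as covariates". The note under Table 40 agrees: "Linear regression model: Mean DU -Volume flow (VF) measured in one leg at 3 months = intercept + Mean-VF (Baseline) + Treatment + Centre", and so on. Neither table shell has a Time row.
- **SAP 8.3.1, next paragraph.** "Laser Doppler Flowmetry (LDF), Duplex ultrasonography (DU) measurements, (Mean Volume Flow and Mean Time Average Mean Velocity) and Ankle Brachial Pressure Index (ABPI") for each ankle "from the Haemodynamic assessment will be analysed using separated Analysis of Covariance (ANCOVA) models". The sentence after it gives covariates for LDF and ABPI only.
- **Protocol 8.3.2.** Flow at 3 months is to be compared by multi-level regression, to allow for repeated measurements.

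The visit schedules (protocol 5.7, SAP 5.8.1) place duplex at baseline and 3 months only. Under SAP 7.4 and the note to Table 39, the device arm's value is the mean of five readings: rest, 15 and 30 minutes into use, and 1 and 5 minutes after. Controls contribute resting values only. This holds at both visits.

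**The concern.** Time and Time*Treatment need at least two outcome occasions. With baseline as a covariate, duplex has one. An analyst who follows Table 2 must either drop the two terms or use the baseline reading as an outcome as well. The second course puts baseline on both sides of the equation, treats two rows from one patient as independent, and changes what the Treatment row means.

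At stake is one of the two mechanistic measures. A reader who looks for the device effect in the Treatment row could be looking at a baseline contrast. With several models on paper and none named as governing, the choice could also be made after the data are seen.

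**Working it through.** **Inputs.** The test is two-sided at 5% (SAP section 8). The size is 86 per arm (SAP 5.7). That figure belongs to AWD and reproduces: for 60 m and SD 120 m, a t-based calculation gives power 0.8999 at 85 per arm and 0.9032 at 86. The documents give no SD, effect or power for duplex, so everything below is in SD units and assumes a baseline to 3-month correlation rho of 0.3, 0.5 or 0.7. Dx and Dy are the arm differences at baseline and at 3 months.

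**1. Only 3-month rows as outcomes.** Time is constant and Time*Treatment duplicates Treatment. The design matrix is two columns short of full rank. Dropping both columns leaves the Table 40 model.

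**2. Baseline and 3-month rows stacked, Time = 0 at baseline.** The slope on baseline is 1 in the baseline rows and rho in the 3-month rows, so the pooled slope is b = (1 + rho)/2. Then:

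- Treatment row = (1 - b) × Dx
- Time*Treatment row = Dy - Dx

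With Dx = 0 the Treatment row is 0 for any Dy. Simulation with Dy = 0, 0.5 and 1 SD gave a mean of 0.00, with p < 0.05 in 0% of runs, at each rho. With Dx = 1 and rho = 0.5 it is (1 - 0.75) × 1 = 0.25 SD.

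**3. Other Time codings (Dx = 0, Dy = 1, rho = 0.5).** With 3 months as the reference the Treatment row is 1.00; with Time centred it is 0.50. The SAP does not state the coding for duplex.

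**4. Standard error of the interaction row.** The true variance of Dy - Dx is (2/n) × 2(1 - rho) = 4(1 - rho)/n, with n per arm. The residual variance is (1 - b)² in baseline rows and 1 - 2b·rho + b² in 3-month rows. Their average is (1 - rho)(3 + rho)/4, so the model reports a variance of (1 - rho)(3 + rho)/n. The ratio of reported to true SE is therefore √((3 + rho)/4). Type I error is the two-sided normal tail beyond 1.96 times that ratio.

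| rho | SE ratio | Type I error, formula | Type I error, simulation |
|---|---|---|---|
| 0.3 | √(3.3/4) = 0.908 | 7.5% | 7.7% |
| 0.5 | √(3.5/4) = 0.935 | 6.7% | 7.0% |
| 0.7 | √(3.7/4) = 0.962 | 5.9% | 6.2% |

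For an assumed true effect of 0.5 SD with arms equal at baseline, simulated power at rho 0.3/0.5/0.7 is 83/93/99% for the interaction row and 92/97/99.6% for the 3-month model, whose type I error is 4.7-5.0%.

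**5. Does the Table 40 model suffice?** Its Treatment row estimates Dy - rho × Dx. With Dx = 0 that is the 3-month effect. But the device arm's baseline mean includes readings with the device on, so Dx need not be 0. Suppose the device has only an acute effect, shifting the mean by D at both visits, with no lasting change. The row is then D(1 - rho):

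- D = 0.5, rho = 0.5: 0.25 SD. SE = √(0.75 × (2/86 + 0.25/172)) = 0.136, so z = 1.84 and p < 0.05 in about 45% of trials (44% in simulation).
- D = 1, rho = 0.5: 0.50 SD, with p < 0.05 in 91% of simulated trials.

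A shift of this size is plausible. Protocol 1.6 cites an 84% flow rise with another stimulation device in healthy people. Applied to the two device-on readings alone, it moves the five-reading mean by (2/5) × 84% = 33.6%. With an assumed coefficient of variation of 60% to 30%, that is 0.56 to 1.12 SD.

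**The case against.** The best defence is that Table 2 is a summary, while 8.3.1 and the shells in Tables 40 and 42 agree with each other and carry no Time rows, so the planned output would come from the 3-month model. The notes to Tables 22 and 24 define time over follow-up visits only. On that convention the duplex Time terms are simply redundant. The ANCOVA mention is weak evidence of another model: regressing a 3-month value on baseline and treatment is itself an ANCOVA, the following sentence omits duplex, and no duplex ANCOVA shell exists.

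Most of this stands. The 3-month model is probably the intended one, and the ANCOVA phrase is a stray. It does not clear Table 2, which is offered as the plan for every endpoint and cannot be fitted as written without a choice that the SAP leaves open. Table 2 also lists duplex at baseline and 3 months where its AWD, ICD and quality-of-life rows list follow-ups only, which invites stacking. That clue is limited, because the LDF and ABPI rows list baseline too.

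A reader might infer that the Treatment row must be about zero whatever the device does. The documents do not support that. It requires stacked rows, Time = 0 at baseline and arms equal at baseline. The SAP states neither the stacking nor the coding, and its own measurement definition makes unequal arms likely if the device acts acutely. Nor is the effect lost from the stacked model, since the interaction row carries Dy - Dx.

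It is also fair to object that deleting the Time terms alone would not repair the endpoint. Step 5 shows this, and the fix allows for it.

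**Conclusion.** The Table 2 duplex model is wrong as written and conflicts with 8.3.1 and Tables 40 and 42; the protocol's multi-level regression is left unreconciled. Read one way, two terms cannot be estimated. Read the other way, with Time = 0 at baseline, the Treatment row is (1 - rho)/2 times the baseline difference, and the interaction row rejects a true null about 6-8% of the time instead of 5%. Those rates assume 86 per arm and correlations of 0.3-0.7, since the documents give no duplex variability or effect.

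The 3-month model is the right one to keep, but only with the same reading in both arms. As the value is now defined, a purely acute effect of 0.5 SD would appear as 0.25 SD at correlation 0.5. The correction should be made. It touches a secondary, mechanistic endpoint and alters no sample-size or primary-endpoint figure.

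**What to change.** Amend the SAP before database lock:

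1. In the Table 2 duplex row, delete Time and Time*Treatment, leaving the 3-month value on baseline, treatment, centre, group, age, gender and BMI, as in 8.3.1 and Tables 40 and 42.
2. In 8.3.1, remove duplex from the ANCOVA sentence.
3. State that Treatment is the coefficient of interest.
4. Record that this replaces the multi-level regression of protocol 8.3.2, with the reason.
5. In 7.4 and Tables 39-42, define both the outcome and the baseline covariate as the resting reading, which is taken in both arms at both visits. Summarise the during-use and after-use readings separately, within the device arm.

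The cost is a few lines of text. No new data are needed, because the resting readings are already scheduled.
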